4.4 Handling of measurements obtained at the early withdrawal visit

Subjects who withdraw early from the study for any reason, including those withdrawn from IMP, will be asked to return for the study assessments 12 weeks after the first dose of IMP (ie, the Week 12 Visit) and will then enter the SFU Period and will undergo the same assessments performed at the SFU Visit (20 weeks after the last dose of IMP).

For subjects who return for the EW visit at any time other than the Week 12 visit, the following rules will apply with regard to the inclusion of the results obtained at the EW visit in the descriptive summaries and in the data listings:

- Any measurements conducted at the EW visit should be included in the summaries for the respective scheduled visit, if the EW visit occurs at the time of the next scheduled visit. For example, if the EW visit occurs on Day 42, the results would be summarized together with the Visit 6 (Week 6, Day 42) results.
- If the EW visit does not correspond to the day of a scheduled visit, the assessments of the EW visit should be mapped to the nearest scheduled visit, relative to the Baseline visit date, following the last scheduled visit where assessments are available
- If the date of the EW visit is equidistant between 2 scheduled visits at which no scheduled assessments were performed, the assessments from the EW visit will be mapped to the earliest of these visits.
- If an EW visit mapping results in data being mapped to a visit where the specific assessment is not actually collected per the protocol schedule of assessments, these data will not be included in the summary statistics and will be listed only
- The only exception to the above rule is for anti-BKZ antibody assessments, in which all early withdrawal visit assessments will be assigned to the next scheduled visit at which anti-BKZ antibodies are assessed. The rationale for this is that anti-BKZ antibody positivity is summarized over a given study period. As part of that summary, a table indicating the first visit at which anti-BKZ antibody positivity is observed will be presented. In order to match the number of subjects who were anti-BKZ antibody positive at specific visits with the overall positivity for the period, it is necessary to ensure that anti-BKZ antibody positivity is attributed to a visit where anti-BKZ antibody assessments were performed.

Assessments from the EW visit will be displayed as the mapped visit and will be flagged in the by-visit data listings

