	Scr. ^a	Baseline Day 1 ^b	Week 2 (±3 days) ^c	Week 4 (±3 days) ^c	Week 5 (±3 days) ^c	Week 6 (±3 days) ^c	Week 7 (±3 days) ^c	Week 8 (±3 days) ^c	Week 9 (±3 days) ^c	Week 10 (±3 days) ^c	Week 12 (±3 days) ^c	Week 30 (-3 to +7 days) ^c
Lesional and nonlesional skin biopsy		X									X	
Photography and thermography ^o		X		X				X			X	
Lesion count (including Hurley Stage) ^p	X	X	X	X		X		X		X	X	X
Modified Sartorius score		X									X	
Erythema assessment	X	X	X	X		X		X		X	X	X
PGA of Skin Pain		X	X	X		X		X		X	X	X
Hidradenitis Suppurativa-Physician's Global Assessment		X	X	X		X		X		X	X	X
DLQI		X	X	X		X		X		X	X	X
EQ5D		X	X	X		X		X		X	X	X
HADS	X	X	X	X		X		X		X	X	X
C-SSRS	X	X	X	X		X		X		X	X	X
Adverse events	X	X	X	X	X	X	X	X	X	X	X	X
Subject identification number assigned ^q	X											

Table 5–1: Schedule of study assessments

Procedures	Screening Period	Treatment Period										SFU Period
	Visit 1	Visit 2	Visit 3	Visit 4	Visit 5	Visit 6	Visit 7	Visit 8	Visit 9	Visit 10	Visit 11	Visit 12/ SFU Visit/EW Visit
	Scr. ^a	Baseline Day 1 ^b	Week 2 (±3 days) ^c	Week 4 (±3 days) ^c	Week 5 (±3 days) ^c	Week 6 (±3 days) ^c	Week 7 (±3 days) ^c	Week 8 (±3 days) ^c	Week 9 (±3 days) ^c	Week 10 (±3 days) ^c	Week 12 (±3 days) ^c	Week 30 (-3 to +7 days) ^c
Randomization ^r		X										
IMP treatment ^s		X	X	X	X	X	X	X	X	X		

ADA=anti-drug antibody; BMI=body mass index; CAT=Computed Axial Tomography; C-SSRS= Columbia-Suicide Severity Rating Scale; DLQI=Dermatology Life Quality Index; ECG=electrocardiogram; EQ-5D=European Quality-of-Life 5 dimensions questionnaire; EW=Early Withdrawal; HADS=Hospital Anxiety and Depression Scale; HiSCR=Hidradenitis Suppurativa Clinical Response; HIV=human immunodeficiency virus; IGRA=interferon-gamma release assay; IMP=investigational medicinal product; PD=pharmacodynamics; PGA=Patient's Global Assessment; PK=pharmacokinetics; RNA=ribonucleic acid; Scr.=Screening; SFU=Safety Follow-Up; TB=tuberculosis

Note: For subjects who prematurely terminate or complete the study, final study disposition will be recorded at the Early Withdrawal Visit. All subjects who prematurely terminate the study, including those withdrawn from IMP, will be asked to return for study assessments 12 weeks after the first dose (ie, the Week 12 Visit) and for an EW Visit that will comprise the same assessments as planned for the SFU Visit (Visit 12; 20 weeks after the last dose of IMP).

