^a The Screening Period will last ≥ 2 weeks up to a maximum of 4 weeks prior to randomization (dosing cannot occur earlier than 2 weeks after Screening due to IMP shipping timelines).

^b Day 1 is defined as the first day of administration and Day -1 is defined as the day before Day 1. Baseline (Visit 2) will include a visit window of ± 2 days for all assessments prior to the first dose of IMP.

^c Visit windows of ± 3 days from the first dose at all visits except SFU. The SFU Visit window is -3 and +7 days from last dose.

^d Will include lifestyle, childbearing potential, as applicable, height, and BMI.

^e Ensure no significant changes in medical history and concomitant disease.

^f Will include an evaluation of signs and symptoms of active TB and risk of exposure to TB at Screening and the SFU Visit (Visit 12).

^g Vital signs (blood pressure, pulse rate, and temperature) are to be measured prior to blood sampling, and prior to dosing, where applicable.

^h Pregnancy testing will be serum testing at Screening and the SFU Visit (Visit 12). The pregnancy test will be urine at all other visits.

ⁱ Subjects with HIV infection or who have evidence of, or tested positive for hepatitis B or hepatitis C virus are excluded. A positive test for the hepatitis B virus is defined as: 1) positive for hepatitis B surface antigen; or, 2) positive for anti-hepatitis B core antibody. A positive test for the hepatitis C virus is defined as: 1) positive for hepatitis C antibody, and 2) positive via a confirmatory test for hepatitis C virus (for example, hepatitis C virus polymerase chain reaction).

^j A chest x-ray must be performed at Screening or must occur within 3 months prior to Screening and results must be available at Baseline. A CAT scan of chest at Screening or within 3 months prior to Screening is acceptable, if available.

^k It is recommended that the QuantiFERON TB GOLD test be performed.

^l All blood samples taken prior to dosing.

^m The PD variables measured include: cytokines, complement, candidate biomarker analysis, and flow cytometry. The nonhereditary pharmacogenomics variables include RNA, proteins, and metabolites biomarkers.

ⁿ A separate Informed Consent Form will be required for subjects who decide to participate in the pharmacogenetic substudy. The Informed Consent Form must be signed prior to collecting any samples for the substudy.

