4.2 Handling of dropouts or missing data

4.2.1 Efficacy data

There will be no imputation of missing data for the individual components of the HiSCR (abscess count, inflammatory nodule count and draining tunnel (fistula/sinus tract) count).

For subjects with a missing HiSCR due to missing component data at a specific visit, or due to early discontinuation from the study during the Treatment Period, non-responder imputation

(NRI) will be used for the primary analysis of the primary efficacy variable. These subjects will be defined as non-responders at a specific visit or at all subsequent visits after the time of study discontinuation. In additional sensitivity analyses, an ‘observed cases’ analysis will also be performed (no imputation of missing HiSCR) and subjects who receive specific rescue therapy will also be considered a non-responder from the time that the rescue therapy was taken to the end of the Treatment Period ([Section 8.2.3](#)).

For the hsCRP data, measurements that are below the limit of quantification (BLQ) will be imputed with half of the lower limit of quantification (LLOQ) for the purpose of calculating summary statistics, changes from Baseline and ratio to Baseline.

The handling of any missing data for the other exploratory efficacy data is described or referenced in the respective sections where the analysis of this data is described.

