4.3 Handling of repeated and unscheduled measurements

All repeated and unscheduled measurements will be presented in the data listings, where applicable. The following general rules will apply to all repeated and unscheduled measurements:

- For repeated measurements obtained prior to the first dose of IMP the latest value (which may be scheduled or unscheduled) will be used in the calculation of the descriptive statistics
- For repeated measurements obtained at the designated Baseline visit, the latest value (which may be scheduled or unscheduled) will be defined as the Baseline provided that this occurred prior to the first dose of IMP
- For repeated measurements obtained at any time point after the first dose of IMP, the values will not be included in the calculation of descriptive statistics or changes from Baseline.
- Unscheduled measurements performed for the Early Withdrawal (EW) visit will be assigned to the appropriate visit ([Section 4.4](#)) and analyzed accordingly

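### The early-withdrawal mapping rule has no distance limit, so a lesion count well outside the Week 12 window can be filed as Week 12, and the SAP does not say that non-responder imputation takes precedence

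*SAP*

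**What the plan says.** SAP 4.4 covers subjects whose EW visit is not the Week 12 visit. If the EW visit does not fall on a scheduled day, "the assessments of the EW visit should be mapped to the nearest scheduled visit, relative to the Baseline visit date", and the candidates are restricted to visits "following the last scheduled visit where assessments are available". If the date is equidistant between two visits, "the assessments from the EW visit will be mapped to the earliest of these visits". Data mapped to a visit where that assessment is not scheduled are listed only. The lead-in gives the scope of these rules as inclusion "in the descriptive summaries and in the data listings".

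SAP 4.3 adds: "Unscheduled measurements performed for the Early Withdrawal (EW) visit will be assigned to the appropriate visit". It points to 4.4 and says the values are then analysed on that basis.

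SAP 4.2.1 prescribes non-responder imputation (NRI) for the primary analysis, for subjects whose HiSCR is missing because of missing components or early discontinuation: "These subjects will be defined as non-responders at a specific visit or at all subsequent visits after the time of study discontinuation". Protocol 15.10 lists missing data and early study discontinuation in the Treatment Period as separate grounds. It makes discontinuers non-responders at every later visit.

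The protocol's visit window is ±3 "days from the first dose at all visits except SFU" (Table 5-1, footnote c). Table 5-1 schedules lesion counts at Week 10, Week 12 and the combined SFU/EW visit. Its note describes "an EW Visit that will comprise the same assessments as planned for the SFU Visit (Visit 12; 20 weeks after the last dose of IMP").

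**The concern.** A nearest-visit rule without a maximum distance works when visits are close together. Here the visit after Week 12 is Week 30, so Week 12 takes in a long stretch of follow-up. It also takes in the days just after Week 10, because a visit that already has data is no longer a candidate. The listed-only exception gives no protection, because lesion counts are scheduled at Week 12.

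A subject who attends Week 10 and has an EW visit on Day 73 is 3 days from Week 10 and 11 days from Week 12, yet the count is filed as Week 12. An EW visit on Day 120 is 36 days from Week 12 and 90 from Week 30, and is also filed as Week 12.

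Two things are at stake. First, Week 12 summaries may contain counts that are not Week 12 counts. Second, a mapped count makes the Week 12 HiSCR non-missing, while SAP 4.2.1 starts from a missing HiSCR. Two programmers could then classify the same withdrawn subject differently on the primary endpoint.

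**Working it through.** **Inputs**
- Day convention: SAP 4.4 gives Week 6 as Day 42.
- Scheduled visits: Weeks 10, 12 and 30 (protocol Table 5-1 and 5.1.2).
- Window: ±3 days (Table 5-1, footnote c).
- Group sizes and placebo prior: 40 bimekizumab, 20 placebo, 20 adalimumab; Beta(5.52, 14.48), worth about 20 subjects (SAP 2.4).

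**Reproducing the plan's own figure.** Day = 7 × week gives 7 × 6 = 42, as stated. Hence Week 10 = Day 70, Week 12 = Day 84 and Week 30 = Day 210. The Week 12 window is 84 ± 3 = Days 81-87, which is 7 days.

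**Upper end of the range.** The midpoint of Weeks 12 and 30 is (84 + 210)/2 = 147. A tie goes to the earlier visit, so Day 147 maps to Week 12. That is 147 − 84 = 63 days, or 9 weeks, after Week 12.

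**Lower end of the range**
- Week 10 data present: Week 10 is not a candidate, so every day from 71 maps to Week 12.
- Week 10 data absent: the midpoint of Weeks 10 and 12 is (70 + 84)/2 = 77. Day 77 is a tie and goes to Week 10, so the range starts at Day 78.
- Week 12 data present: nothing maps to Week 12.

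| Situation (Week 12 missing) | EW days filed as Week 12 | Length | Outside Days 81-87 |
|---|---|---|---|
| Week 10 data present | 71-147 | 77 days | 70 days |
| Week 10 data absent | 78-147 | 70 days | 63 days |

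If the first dose is Day 1, as in SAP 3.2.1.1, Week 12 is Day 85. The ranges become 72-148 and 79-148, with the same lengths.

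**Weight of one subject**
- Raw rate: 1/20 = 5 points on placebo (or adalimumab); 1/40 = 2.5 points on bimekizumab.
- Placebo posterior mean, without the Hurley term: (5.52 + y)/(20 + 20), so one response moves it by 1/40 = 2.5 points.

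**Could one subject change the conclusion?** This was checked with a simplified model: the placebo prior above, a near-vague Beta prior for bimekizumab and no Hurley term. With 6/20 placebo responders, the posterior probability that bimekizumab is better is 0.976 at 20/40 bimekizumab responders and 0.960 at 19/40. One subject can therefore cross the 0.975 threshold, but only if the result already lies there. At 25/40 the probability is 0.999, and the planning rate of 70% corresponds to 28/40.

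**The case against.** A reader might infer that the SAP instructs the analyst to let a mapped EW count replace NRI in the primary analysis. The documents do not support that.
- The 4.4 lead-in limits the mapping to summaries and listings.
- SAP 8.2.2.4 sends missing data in the primary analysis to 4.2.1, not to 4.4.
- Under protocol 15.10, discontinuing the study in the Treatment Period is itself a ground for non-response. SAP Section 1 keeps the protocol's analysis unless the SAP specifies otherwise, and nothing in 4.3 or 4.4 says that mapping overrides NRI.

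A reader might also infer that any subject dosed only at Baseline who attends 20 weeks later (Day 140, window Days 137-147) becomes a Week 12 case. The Table 5-1 note allows that reading. However, the pregnancy and tuberculosis sections (protocol 11.1.4, 11.3.1 and 11.3.1.4) treat the EW and SFU visits as separate. Even on the wider reading it works only for a single dose: with a last dose at Week 2, the 20-week visit is Day 154 (window 151-161) and maps to Week 30.

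Two further points carry weight. The primary analysis uses the PPS, and visit-schedule deviations are a class of important deviation (SAP 3.4), so some of these subjects may be excluded. And ±3 days is a scheduling window: the SAP sets no such analysis window for regular Week 12 visits.

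These objections narrow the point but do not remove it. The by-visit HiSCR tables (SAP 8.2.5), the AN count of 0, 1 or 2 (8.3.1.1) and the pain responders (8.3.3) lie within the stated scope of 4.4. SAP 4.3 goes beyond description. The observed-case analyses (8.2.3.3 and 8.2.3.8) apply no NRI that could set a mapped value aside. The PPS criteria are in a separate document, and SAP 8.2.3 repeats all these analyses on the FAS.

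**Conclusion.** The mapping rule is too wide for Week 12. In the summaries it expressly governs, it accepts EW counts over 70 or 77 days against a 7-day window. Through SAP 4.3 it plausibly reaches the observed-case and FAS analyses too. For the primary analysis the finding is an unresolved question of precedence, not an instruction that conflicts with NRI. If a mapped value were used there for a subject who discontinued the study in the Treatment Period, it would contradict protocol 15.10.

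The likely size is small. The problem needs a missing Week 12 visit and an EW count in the range above, and PPS review may remove some cases. Each one is worth 5 points on the raw placebo rate or 2.5 points on the bimekizumab rate. The documents give no basis for estimating how many subjects are affected, or whether the number differs by arm. The day ranges assume that Week 30 counts as a scheduled visit for mapping and that Week 6 is Day 42, as in the SAP's example.

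**What to change.** Make two additions to the SAP.

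1. In 4.2.1, with a cross-reference from 4.3: EW mapping never overrides NRI. A subject who discontinues the study during the Treatment Period is a non-responder at all later visits, whether or not an EW lesion count has been mapped to one of them.
2. In 4.4: an EW lesion count may supply a Week 12 value, in observed-case analyses and by-visit summaries, only if it was taken within ±3 days of Week 12, or within the tolerance that the data evaluation meeting accepts for regular Week 12 visits. Otherwise it is listed only. Express the limit as days after first dose, because SAP 3.2.1.1 numbers the first dose as Day 1 while the example in 4.4 puts Week 6 at Day 42.

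Allowing the data evaluation meeting's tolerance avoids holding an EW count to a stricter standard than a regular Week 12 visit on the same day. The cost is two short SAP statements and one programming condition. The downside is that a few early or late EW counts drop out of the Week 12 summaries; they remain in the listings.

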5.2 Schedule of study assessments

A schedule of study assessments is provided in [Table 5–1](#).

PUBLIC COPY
This document cannot be used to support any marketing authorization application and any extensions or variations thereof.

Table 5–1: Schedule of study assessments

Procedures	Screening Period	Treatment Period										SFU Period
	Visit 1	Visit 2	Visit 3	Visit 4	Visit 5	Visit 6	Visit 7	Visit 8	Visit 9	Visit 10	Visit 11	Visit 12/ SFU Visit/EW Visit
	Scr. ^a	Baseline Day 1 ^b	Week 2 (± 3 days) ^c	Week 4 (± 3 days) ^c	Week 5 (± 3 days) ^c	Week 6 (± 3 days) ^c	Week 7 (± 3 days) ^c	Week 8 (± 3 days) ^c	Week 9 (± 3 days) ^c	Week 10 (± 3 days) ^c	Week 12 (± 3 days) ^c	Week 30 (-3 to +7 days) ^c
Written informed consent	X											
Demographics and Baseline characteristics ^d	X											
Inclusion/exclusion criteria verification	X	X										
Significant past medical history and concomitant diseases	X	X ^e										
Hidradenitis suppurativa history	X											
Concomitant medications	X	X	X	X	X	X	X	X	X	X	X	X
Physical examination ^f	X	X	X	X		X		X		X	X	X
Body weight	X	X									X	X
Vital signs ^g	X	X	X	X	X	X	X	X	X	X	X	X
12-lead ECG	X	X		X				X			X	X
Pregnancy test ^h	X	X		X				X			X	X
Urine drug screen	X											
Hematology, biochemistry, urinalysis	X	X		X				X			X	X

Table 5–1: Schedule of study assessments

Procedures	Screening Period	Treatment Period										SFU Period
	Visit 1	Visit 2	Visit 3	Visit 4	Visit 5	Visit 6	Visit 7	Visit 8	Visit 9	Visit 10	Visit 11	Visit 12/ SFU Visit/EW Visit
	Scr. ^a	Baseline Day 1 ^b	Week 2 (±3 days) ^c	Week 4 (±3 days) ^c	Week 5 (±3 days) ^c	Week 6 (±3 days) ^c	Week 7 (±3 days) ^c	Week 8 (±3 days) ^c	Week 9 (±3 days) ^c	Week 10 (±3 days) ^c	Week 12 (±3 days) ^c	Week 30 (-3 to +7 days) ^c
Serology (HIV, Hepatitis B and C virus) ⁱ	X											
Chest x-ray or CAT scan of chest ^j	X											
TB questionnaire	X	X									X	X
IGRA TB test ^k	X											X
Blood sampling for plasma PK levels of bimekizumab ^l		X	X	X				X			X	X
Blood samples for PD and nonhereditary pharmacogenomic variables ^m		X						X			X	
Blood samples for pharmacogenetic variables ⁿ		X									X	
Blood samples for plasma levels of bimekizumab ADA ^o		X	X	X				X			X	X
Urine samples for biomarker research		X									X	

Table 5–1: Schedule of study assessments

Procedures	Screening Period	Treatment Period										SFU Period
	Visit 1	Visit 2	Visit 3	Visit 4	Visit 5	Visit 6	Visit 7	Visit 8	Visit 9	Visit 10	Visit 11	Visit 12/ SFU Visit/EW Visit

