11.2 Adverse events

Adverse events with a start date prior to the first dose of IMP will be defined as pre-treatment AEs. A treatment-emergent AE (TEAE) is defined as any AE with a start date/time at the time of or after the first dose of IMP up until 140 days after the last dose of IMP. Any AE with onset later than 140 days after the last dose of IMP will not be considered as treatment-emergent and therefore will not be included in the tabulations of TEAEs. Where dates are missing or partially missing, AEs will be assumed to be treatment-emergent, unless there is clear evidence to suggest that the AE started prior to the first dose of IMP or later than the defined cutoff for TEAEs.

Handling of missing dates/times for classification of AEs as TEAEs is described in [Section 4.2.4](#).

All AEs will be recorded in the eCRF from informed consent until study completion or termination. All AEs will be coded and categorized by intensity (mild/moderate/severe) and relationship to IMP (related/not related).

An overview of the number and percentage of subjects who experience TEAEs will be presented by treatment group, based on the SS. This tabulation will include the number and percentage of subjects with any TEAEs, serious TEAEs, related TEAEs, discontinuation due to TEAEs, severe TEAEs, AEs leading to death and TEAEs leading to death; event counts will also be included.

In addition, the following summaries will be presented by treatment group, SOC, high level term (HLT) and PT, based on the SS:

- Incidence of TEAEs
- Incidence of TEAEs, stratified by overall anti-BKZ antibody status (positive/negative) as defined in [Section 10](#)
- Incidence of serious TEAEs
- Incidence of non-serious TEAEs
- Incidence of TEAEs by relationship
- Incidence of TEAEs by maximum relationship
- Incidence of TEAEs by maximum intensity
- Incidence of fatal TEAEs by relationship
- Incidence of non-serious TEAEs by relationship
- Incidence of serious TEAEs by relationship
- Incidence of non-serious TEAEs above threshold of 5% of subjects
- Incidence of non-serious TEAEs above threshold of 5% of subjects by relationship
- Incidence of TEAEs by SOC and PT (including the number and percentage of subjects and individual subject numbers for each PT stratified by intensity, relationship and seriousness)

In addition, separate summaries by treatment group, SOC, HLT and PT will be included for the following AEs for special monitoring (AESM):

- Major cardiovascular events

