11.3 Clinical laboratory evaluations

Laboratory data (chemistry, hematology and urinalysis) and changes from Baseline (if applicable) for numeric variables will be listed by treatment group and visit. Any laboratory variables that are BLQ or ALQ will be handled as described in [Section 4.2.3](#). Values outside the

reference range for the numeric variables will be flagged in the listings and in addition, will be listed separately. The reference ranges will also be reported in the listings.

Chemistry and hematology variables presented in [Table 11–1](#) will be summarized by treatment group at each visit, for both observed values and changes from Baseline. Figures of mean and mean change from Baseline will be presented by treatment for the absolute neutrophil count (ANC). All treatment groups will be overlaid on the same plot and the plot will include the error bars based on the SD (ie, mean +/-SD).

Laboratory variables will be grouped according to the laboratory function panel and categorized as normal, high or low, if applicable, based on the reference range supplied by the analytical laboratory. For selected variables that are identified in [Table 11–1](#), the change in category from Baseline will be presented in shift tables for all post-Baseline visits.

The number and percentage of subjects with treatment-emergent markedly abnormal (TEMA) values will be tabulated by treatment group and visit. Markedly abnormal laboratory values will generally be defined as those categorized as Grade 3 or Grade 4 as per the Rheumatology Common Toxicity Criteria (RCTC) Version 2.0 (Woodworth et al, 2007). Communication with the lead author of the RCTC publication has revealed that the reference ranges for absolute lymphocyte counts (ALC) are in error, therefore ALC criteria will follow the ranges defined as per the Common Terminology Criteria for Adverse Events (CTCAE) Version 4.03 (United States Department of Health and Human Services, 2010). Additional laboratory variables (not present in the RCTC publication) will also be categorized as per the CTCAE Version 4.03. The criteria for identifying TEMA values are presented in [Table 14–7](#) and [Table 14–8](#) for hematology and chemistry values respectively.

Laboratory measurements meeting the criteria for TEMA will be listed separately for hematology and chemistry. The listings will include all measurements for any variable with at least 1 TEMA result for each subject

Table 11–1: Laboratory measurements

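### Laboratory and ECG results from early-withdrawal visits mapped to 6 of the 9 post-Baseline treatment visits are listed only, so they miss the markedly-abnormal and QTcF counts

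*SAP*

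**What the plan says.** SAP 4.4 deals with an EW visit held at any time other than Week 12. If it does not fall on a scheduled visit day, its assessments are "mapped to the nearest scheduled visit, relative to the Baseline visit date, following the last scheduled visit where assessments are available". Where the mapped visit does not schedule a given assessment, "these data will not be included in the summary statistics and will be listed only". One carve-out follows: "The only exception to the above rule is for anti-BKZ antibody assessments", which go to the next visit that collects them. Mapped EW results are flagged in the by-visit listings.

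The Protocol (note to Table 5-1) asks those who leave early to return at Week 12 and "for an EW Visit that will comprise the same assessments as planned for the SFU Visit". The SFU column includes the row "Hematology, biochemistry, urinalysis" and the 12-lead ECG.

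Two safety tables depend on the assigned visit. SAP 11.3 states: "The number and percentage of subjects with treatment-emergent markedly abnormal (TEMA) values will be tabulated by treatment group and visit". SAP 11.4.2 tabulates QTcF categories by treatment group and visit, with subjects measured at that visit as the denominator. The liver-abnormality table (SAP 11.3, Table 14-9) is different: it counts subjects abnormal at any visit after Baseline.

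SAP 4.3 adds that repeat measurements taken after the first dose do not enter descriptive statistics or changes from Baseline.

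**The concern.** Safety is part of the secondary objective. The TEMA and QTcF counts are where a reader looks for the frequency of notable laboratory and ECG abnormalities. A sample taken when a subject leaves the study can be the most informative one for that subject. Under SAP 4.4, whether it reaches those counts depends on which scheduled visit comes next, not on what the sample shows.

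The repeat-value rule acts in the same direction. Protocol 6.3 (criterion 10) bases withdrawal for persistent Grade 2 laboratory results on retests, and Protocol 11.2.1 requires repeat liver tests. Values of this kind can therefore lie outside the by-visit summaries.

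**Working it through.** **Inputs**

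- Post-Baseline Treatment Period visits (Protocol Table 5-1): Weeks 2, 4, 5, 6, 7, 8, 9, 10, 12, which is 9 visits.
- Visits among these with safety laboratory tests and ECG (Protocol 8.3 to 8.9): Weeks 4, 8, 12, which is 3 visits.
- Mapping rule: SAP 4.4. If every earlier visit was attended, the nearest scheduled visit after the last attended one is simply the next visit.

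**The SAP's own example.** SAP 4.4 says an EW visit on Day 42 is summarized with Week 6. Protocol 8.6 lists neither laboratory tests nor ECG at Week 6. By the later bullet of the same section, this example subject's laboratory and ECG results are listed only.

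**Count by visit.** 9 − 3 = 6 visits without laboratory tests or ECG (Weeks 2, 5, 6, 7, 9, 10). 6/9 = 67%.

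**Count by calendar day** (visit day = 7 × week; all earlier visits attended):

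| Day of EW visit | Mapped to | Days | Labs/ECG scheduled there |
|---|---|---|---|
| 1–14 | Week 2 | 14 | no |
| 15–28 | Week 4 | 14 | yes |
| 29–35 | Week 5 | 7 | no |
| 36–42 | Week 6 | 7 | no |
| 43–49 | Week 7 | 7 | no |
| 50–56 | Week 8 | 7 | yes |
| 57–63 | Week 9 | 7 | no |
| 64–70 | Week 10 | 7 | no |
| 71–84 | Week 12 | 14 | yes |

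Listed only: 14 + 5 × 7 = 49 days. Summarized: 14 + 7 + 14 = 35 days. 49/84 = 58%.

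**Which tables are touched**

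- TEMA laboratory counts (by visit): listed-only values do not enter.
- QTcF categories (by visit): listed-only values do not enter.
- Liver table (any visit after Baseline): unclear. SAP 4.4 keeps these values out of summary statistics, while SAP 11.3 counts any post-Baseline visit. The SAP does not say which governs.
- Vital signs: collected at every visit, so SAP 4.4 removes nothing.

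**Number of subjects (assumption only).** The documents give no withdrawal rate. If 5% to 15% of 80 subjects (4 to 12) had an EW visit during treatment, the number with listed-only results would be 4 × 49/84 = 2.3 to 12 × 49/84 = 7.0 by calendar day, or 4 × 6/9 = 2.7 to 12 × 6/9 = 8.0 by visit count. Fewer are affected if some who leave have no EW visit during treatment.

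**Weight of one subject.** 1/20 = 5 percentage points in the placebo or adalimumab arm; 1/40 = 2.5 in the bimekizumab arm.

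**The case against.** The strongest reply is that nothing is lost. EW results are listed and flagged. Out-of-range laboratory values get their own listing, and the TEMA listings show all measurements of any variable with a TEMA result for that subject. Potential liver-injury events must also be reported as AEs (Protocol 11.2.1). This stands: a reader who infers that the data disappear goes too far. The gap is in the counts.

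Nor do the documents support saying that these subjects' last on-study results are lost. Those withdrawn from treatment are asked back for Week 12 and SFU; both collect laboratory tests and ECG, and both are summarized. That is a partial safeguard only, because attendance is a request, and Protocol 6.3 directs subjects who withdraw consent to the SFU Visit alone. An EW visit after Week 12 would map to SFU, so over 30 weeks the exposed share is 49/210 = 23%.

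It is also not shown that the affected visits mostly follow safety withdrawals. The Protocol asks for a prompt EW visit for TB or NTMB infection (6.3, 11.3.1), and an EW visit on pregnancy (11.1.4). For AE and laboratory withdrawals, 6.3 refers to Week 12 and SFU.

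The antibody carve-out has its own reason: by-visit first positives must reconcile with positivity over the period. Extending it to laboratory tests and ECG would mix sampling times in the by-visit means, and an EW value moved to Week 12 could collide with a real Week 12 value. This also stands, and it argues for a different remedy.

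**Conclusion.** The point holds for the by-visit TEMA and QTcF counts. Followed as written, the plan leaves out laboratory and ECG results from EW visits mapped to 6 of 9 treatment visits, or 58% of treatment days when all earlier visits were attended. For the liver table the fault is ambiguity, not demonstrated exclusion. The number of subjects rests wholly on an assumed withdrawal rate and on how many EW visits occur during treatment. The primary efficacy analysis is unaffected.

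A reader might infer a second fault from the AE rule in SAP 11.2: "Any AE with onset later than 140 days after the last dose of IMP will not be considered as treatment-emergent". Protocol Table 5-1 adds: "The SFU Visit window is -3 and +7 days from last dose". With SFU due at 20 × 7 = 140 days, permitted visits run from Day 137 to Day 147, and 7 of those 11 days lie past the cut-off. The documents do not make this an error. The cut-off equals five bimekizumab half-lives (5 × 28 = 140, SAP 11.1), and the Protocol defines no treatment-emergent window for it to contradict. Status follows onset, not visit date, so an event found at a late SFU Visit but starting by Day 140 still counts. AEs with missing or partial dates are taken as treatment-emergent unless there is clear evidence otherwise. Ending the period at each subject's SFU date would give subjects unequal risk windows.

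**What to change.** - Keep the by-visit means, changes and counts as planned in SAP 11.3 and 11.4.2.
- Add an any-time post-Baseline row to the TEMA and QTcF category tables. It should count scheduled, EW, repeat and unscheduled values, with each subject counted once per criterion and a stated denominator.
- State in SAP 4.3 and 4.4 that the listed-only and repeat-value rules do not apply to these rows.
- State that the liver table (Table 14-9) counts the same set of values.
- Leave the 140-day window in SAP 11.2 unchanged.

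The cost is a few lines of SAP text and minor programming, with no new data. SAP section 1 already provides for an amendment before database lock. The any-time counts will not equal the by-visit counts, which needs a footnote saying which values each includes.
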